1 PROTOCOL SUMMARY

Title: A comparative study between a pre-hospital and an in-hospital circulatory support strategy (ECMO) in refractory cardiac arrest.

Introduction and hypothesis:

Cardiac arrest (CA) or sudden death affects approximately 40,000 people in France. It is still a major cause of death in a young population. Management of CA is defined by international recommendations, detailed by learned societies in each country. It includes several links that are interconnected for its optimisation. This "survival chain" associates: early alert, early external cardiac massage, early defibrillation, early specialised intensive care and specific hospital management. Despite all these improvements, no progress, or little has been made in the survival of CA victims over the past few years in industrialised countries, and the survival rate in France is 3% to 5%.

Refractory cardiac arrest is defined as failure, after 30 minutes of specialised resuscitation. It used to be the standard to admit that there was no hope of spontaneous cardiac activity and satisfactory neurological recovery after this period, except in cases of CA with neuroprotection (intoxication, hypothermia).

External circulatory support such as "extracorporeal cardiopulmonary resuscitation" (ECPR) makes it possible to replace the circulatory activity of the myocardium and the respiratory activity of the lungs. The indications that are currently recognized in adults are:

- haemodynamic failure due to medical causes or after heart surgery
- respiratory failure (Acute Respiratory Distress Syndrome - ARDS) due to medical causes (infection, etc...) or post-surgery.

This technology was developed over the past 10 years, possibly as a result of several factors. The first is technological with miniaturisation and simplification of ECPR devices. This simplification is associated with an increase in the safety of use resulting from multi-setting monitoring built into ECPR devices.

The second factor is the extension of indications beyond cardiac surgery. In fact, medical intensive care teams are now accustomed to ECPR management without the intervention of cardiovascular surgeons. Specific training enables non-surgeon physicians to use this technique either in a hospital

setting with a cardiac surgery centre, or a network between a hospital without cardiac surgery and a tertiary care centre.

In in-hospital cardiac arrest (CA) some teams use ECPR with an improvement in the survival rate of 20% in comparison to standard resuscitation. This use demonstrates the possibility of neurological recovery independent from the recovery of spontaneous cardiac activity which can be differed.

These results encouraged the use of ECPR in cases of out-of-hospital refractory cardiac arrests. Patients who are victims of CA are resuscitated for 30 minutes on the spot where the CA occurs. They are then transferred to a specialised centre. The significant improvement in survival noted in in-hospital CAs was not observed in the French series of studies concerning out-of-hospital CAs. This survival is currently estimated at 4%. This difference can be partly explained by the difference in time between the beginning of cardiac massage and the implementation of circulatory support by ECMO ("low flow" period). This time period is directly correlated to survival. The French studies find an average period of approximately 120 minutes of low flow which corresponds to approximately 5% survival. This time period can be explained by the time required for the following:

- 30 minutes of specialised resuscitation
- placement on a stretcher
- transport to hospital
- ECMO implementation.

Since 2011 a strategy has been developed to shorten these time periods with the installation of the circulatory support system at the place where the cardiac arrest occurs. This strategy has proven its feasibility.

To demonstrate the superiority of this strategy in terms of survival, we would like to conduct a randomised comparative study of two strategies: 1) ECPR implementation between the 20th minute to the 40th minute of CA, directly at the site of the CA, by emergency physicians and/or specifically trained resuscitators 2) optimised on-site resuscitation with secondary transfer to the hospital for the implementation of support. The purpose is to increase from 5% to 20% the survival of victims of out-of-hospital refractory cardiac arrests with a good neurological prognosis.

Main objective:

The hypothesis is that pre-hospital ECPR will result in survival for 20% of the patients, considering that the percentage of survival with in-hospital ECPR is less than 5%.

Main judgement criterion:

Survival with good neurological outcome (CPC 1 or 2) on discharge from intensive care or at 6 months

Secondary judgement criteria:

Success rate of the implementation of ECPR

ECPR implementation time

Immediate complications: haemorrhage, infection

Number of organ harvesting

The quality of survivors' neurological status according to the CPC neurological classification at D 28, 2 months and 1 year

Predictive indicators of the prognosis during cardiac arrest via cerebral and biological monitoring

Inclusion criteria:

Eligible patients have the following combination of criteria:

- Adults over 18 years of age and under 65 years of age
- **And** Refractory cardiac arrest (defined by the failure of professionals to resuscitate at the 20th minute of cardiac arrest with a minimum of 3 AED or equivalent analyse)
- **And** Beginning of external cardiac massage within the first 5 minutes after cardiac arrest (no flow < 5 min.) **with** persistent shockable rhythm **or** persistent of signs of life during resuscitation (any rhythm): spontaneous movement, absence of mydriasis and/or pupillary response, spontaneous breathing movements
- **And** Medical cause of the cardiac arrest
- **And** ETCO₂ above 10 mm Hg at the time of inclusion
- **And** Absence of major co-morbidity.
- **And** ECPR team available and on-site before the 40th minute

Non-inclusion criteria:

- Children under 18 years of age
- Adults over 65 years of age
- Period of more than 5 minutes without cardiac massage after collapsing
- Known co-morbidity that compromises the prognosis for short or medium-term survival
- Cardiac arrest during transportation times

Methodology, type of study: This is a prospective randomised study of current care

Sample size (SS, power, risk): A total number of 105 patients in each group will make it possible to demonstrate at the alpha risk of 5% and a power of 1- β =90%, a significant difference in favour of early pre-hospital ECPR compared to the current practice with in-hospital ECPR.

Study procedure:

Baseline visit: patient inclusion

When a victim of cardiac arrest with strict "no flow" for less than 5 minutes is taken under care in an out-of hospital setting, a mobile ECPR team is rushed to the spot at the 10th minute of cardiac arrest. The 2 physicians in this team verify the inclusion criteria. The patient is included when all the eligibility criteria are present, between the 20th minute and the 40th minutes of cardiac arrest. Treatment starts immediately after randomisation. The success rate and ECMO implementation time are noted and compared. The family is informed at inclusion or at intensive care arrival. The patient is informed as soon as possible, if he/she is alive.

Follow-up visit on discharge from intensive care, at day 28, at 2, 6 and 12 months.: These visits should evaluate the patient outcome. The CPC score and the number of transfusions and infections during hospitalisation are evaluated.

Duration of the study: 4 years

Participation period for one patient: 1 Year

Number of investigator sites: 4

Expected results: An increase of 5% to 20% of survival for victims of out-of-hospital refractory cardiac arrest, with a good neurological prognosis.

2 STATUS OF THE QUESTION

2.1 Circumstances surrounding the problem:

2.1.1 The limits of conventional resuscitation in cardiac arrests.

Sudden adult death, unexpected cardiac arrest (CA) most often related to cardiovascular causes, affects more than 40,000 people in France every year.

The prognosis of out-of-hospital sudden death is particularly sombre. Only 5 to 20% of the patients survive without neurological sequela. This prognosis can be partially improved by an efficient organisation of management that implements the concept of the "survival chain". An early alert by witnesses of the CA, carrying out the first interventions, cardiopulmonary resuscitation (CPR), defibrillation by the public or persons qualified in first-aid, followed by specialised resuscitation by a medical team (such as the ambulance service) increase the amount of survivors. The reduction in the time that passes before the first interventions (called the no-flow period) and the duration of resuscitation before return of spontaneous circulation (ROSC) called low-flow, are considered to be the primary predictive factors of survival in CA. (1)

Just recently, better knowledge of post-cardiac arrest syndrome (2) also contributed to an improvement in the prognosis and the quality of survival. The introduction of early angioplasty(3)(4) and the generalisation of therapeutic hypothermia(5)(6) now complete management for which coding is steadily improving through international and national recommendations that are updated every 5 years¹ (1). However, in order to show what it is capable of, this conventional management of CA requires spontaneous cardiac activity to be re-established as quickly as possible. Therefore, a return of spontaneous circulation (ROSC) must be obtained in the field in out-of-hospital sudden deaths.

Classically, in the absence of ROSC after 30 minutes of correctly administered resuscitation, the CA is considered to be refractory (7)(8)(9) and the treatment options are limited⁸ (10). Just recently, it was shown that the chances of survival are non-existent after 16 minutes of resuscitation.(11) In most cases, resuscitation is discontinued and the patient is declared dead on the spot. The regulatory

inclusion of a physician on ambulance service teams relieves the difficulty of this decision. It is often simple to make and is medically indisputable when it is obvious that the prognostic factors are very unfavourable (notably, an extended no-flow period) and/or the conditions (advanced age, severe chronic disease, etc...) are not compatible with prolonged resuscitation. This decision is much more difficult when the prognostic factors are favourable and prolonged resuscitation efficiently provides spontaneous circulation (signs of the patient awaking during CPR). Under these circumstances, in France and several other European countries, the decision can be made to continue ECM and transport the refractory CA victim. It was made possible by the development of mechanical external cardiac massage devices such as Autopulse ®(12) and Lucas®(13)(14) which enable prolonged ECM during transport by the emergency service. However, this continuation of resuscitation can only be considered if it enables another subsequent treatment for the patient. Two options are possible. The patient can be declared dead and become a potential organ donor in the framework of an organ harvesting procedure in a patient after "cardiac death". This harvesting, which is highly organised according to regulations, can only be done in certain hospitals authorised by the French Biomedicine Agency.

Or, resuscitation can be prolonged by the use of extracorporeal circulatory support.

2.1.2. The progress of extracorporeal circulatory support and cardiac arrest

Circulatory support is a technique that has been in common use for many years now peri-operatively in cardiac surgery. One of its simplest forms, ECMO (extracorporeal membrane oxygenation) is being used more and more often outside of this field, notably in paediatrics and in the care of ARDS or refractory shock in adults. This technique has notably been widely introduced in general intensive care in the treatment of H1N1 malignant influenzas that affect young subjects(15). In parallel with this extension of the indications for ECMO, the technical development of equipment was a major factor. ECMO devices, which are particularly easy to use, miniaturised and energy autonomous, are available. They make it possible to use ECMO during inter-hospital transport by ambulance or

helicopter. In France, several teaching hospitals have therefore developed mobile teams called UMAC (mobile circulatory support unit) that enable the implementation of ECMO in intensive care units where there was none, and the transport of patients on circulatory and respiratory support to a reference centre. (16)

2.1.3. The implementation of ECMO in CA

It quickly became evident that the possibility of having artificial circulatory activity that enables efficient perfusion by oxygenated blood was important for CA victims whose heart had stopped beating. The term extracorporeal cardiopulmonary resuscitation (ECPR) has since emerged. The first research, conducted primarily during refractory CAs that occurred in the hospital setting, demonstrated the unexpected possibility for survival in patients who, without this option would be dead, and for whom resuscitation would have been stopped. In 2003 in Taiwan, Chen et al. noted a survival rate of almost 30% in a series of CAs that occurred in the hospital setting(17)(18). In Caen, France, the same phenomenon was noted: the survival of 8 out of 40 patients who benefited from ECPR following refractory CA(19). This technique proved to be highly adapted when the cause of the CA was potentially reversible. Mégarbane et al. noted the survival of 3 out of 12 victims of CA following acute intoxication with cardiotoxic drugs(20).

In international recommendations, circulatory support is still only recommended in paediatrics. However, these indisputable successes in adults led to an attempt to rationalise the use of therapeutic ECPR in France (21). The indications considered as possible include the existence of hypothermia, intoxication, signs of life during CPR, and CPR (low-flow) of less than 100 minutes.

The development of ECPR programmes for the treatment of refractory CA demonstrated a difference in prognosis between in-hospital and out-of-hospital CAs. In-hospital CAs quickly benefit from the implementation of ECPR. Out-of-hospital CA victims have late access to this possibility of resuscitation. In fact they require resuscitation of at least 30 minutes in the field to be considered as refractory, followed by transport under mechanical ECM until arrival at a centre with ECPR. Le

Guen et al. noted that in a series of patients who were victims of sudden death in Paris in out-of-hospital settings, only 2 out of 51 patients survived in good neurological condition(22). Most of these patients had extended low-flow periods before the implementation of ECPR. A negative correlation between the duration of resuscitation before ECPR and survival explains this poor prognostic result. In addition, resuscitation prolonged by mechanical ECM is burdened by its own morbidity as Agostinucci et al. emphasized(23). This negative influence before access to ECPR is also noted by Chen et al.(24) in the hospital setting. The prognosis rapidly decreases when resuscitation is prolonged: more than 40% survival if resuscitation lasts less than 30 minutes; 17% when it surpasses 60 minutes. This difference in survival between in-hospital and out-of-hospital CA is also noted in another series of French studies (Gay, AFAR abstract). The prognosis for out-of-hospital CA is even worse when it is accompanied by prolonged CPR. Morbidity is also higher among these patients. Cadarelli et al. included all the research and case histories published up until 2008 in a meta-analysis and demonstrated the harmful effect of prolonged CPR(25). In this analysis, the speed at which ECPR is implemented appears to be a prognostic factor similar to patients' age and the total duration of circulatory support. Therefore, ECPR that is started after more than 30 minutes of CPR results in a decrease in survival. Kilbaught et al.(26) emphasize that it is actually the time factor that makes the difference between in-hospital and out-of-hospital CAs. In their pre-hospital emergency system, very rapid transport of patients during CPR to start ECPR upon arrival in the emergency service is possible. With this strategy, they demonstrate that the difference in prognosis between in-hospital and out-of-hospital CAs is eliminated when the time for implementation of ECPR is comparable. As a result, ECPR is used earlier and earlier in hospitals in Japan with results currently being published that appear to be very positive for survival.

2.1.4 The concepts of pre-hospital ECPR

The analysis of the international literature shows that ECPR might be a management method that improves the survival of CA victims.

However, in the context of out-of-hospital sudden death in a medicalised emergency system and in the framework of French regulations, there are two limiting factors:

- the obligation for resuscitation for 30 minutes before categorically announcing that the CA is refractory and whether or not to choose another treatment option.
- the possibility to have access to ECPR within the closest time period to the 30 minutes of CPR, which appears to be an important threshold in determining the prognosis.

Pre-hospital ECPR, which is the basis of the research concept being proposed, includes arteriovenous cannulation and the implementation of the extracorporeal system (pump, oxygenator) in a non-healthcare setting. It is therefore different from the in-hospital transport of patients on ECPR since the preceding steps take place in a hospital. The implementation of ECPR in hospital studies can be rapid, approximately 20 minutes in the Japanese study series and according to our experience(27). ECPR for out-of-hospital refractory CAs was the subject of a few clinical cases, in children(28) and in sports events(29). Its feasibility by the ambulance service pre-hospital teams was confirmed in our last studies(30)(27).

The improvement in survival with early ECPR, close to a 30-minute period of CPR should also be demonstrated. It is only based on the extrapolation of the results of very fast transport and almost without specialised resuscitation of victims of sudden death close to a hospital with ECPR.

Confirmation of this concept is therefore of particular importance and in fact:

- it would provide the prospect of a new treatment possibility for patients whose chances for survival are extremely slim, because prolonged CPR is required to have access to a hospital ECPR. It is an essential step before conducting a multi-centre randomised study to demonstrate the beneficial effect on survival.

- it would make it possible to stress the pertinence of the French teams' approach in this field, notably in comparison to European countries (Germany, Spain, etc...) that already have a medicalised pre-hospital emergency system, or that are currently developing it, like Japan.

3 RESEARCH OBJECTIVES

3.1 Main objective

Demonstration of an increase by 5% to 20% in survival of victims of out-of-hospital refractory cardiac arrest with a good neurological prognosis at 6 months evaluated by the CPC score.

3.2 Secondary objectives

To evaluate the complications of pre-hospital ECPR.

To evaluate the progression of patients admitted to the ICU.

To identify predictive factors of success of pre-hospital ECPR.

4 JUDGEMENT CRITERIA

4.1 Main judgement criterion

Patient survival with good neurological outcome (CPC 1 or 2) on discharge from the ICU or at 6 months.

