4.2 Secondary judgement criteria

- The complications of pre-hospital ECMO are evaluated by indirect criteria. The criteria chosen are:
 - Percentage of success with the implementation of ECPR. ECPR with an output of more than 2 litres per minute is considered to be successful.
 - ECPR implementation time. The time period taken into account is the time period before incision - the initiation of ECPR
 - The percentage of severe complications due to haemorrhage defined by more than 6 transfusions of packed red blood cells in the first 24 hours
 - The percentage of infectious complications defined by the presence of a systemic inflammatory response associated with a presumed or identified infection during hospitalisation in the ICU.
- The progression of patients admitted to the ICU is evaluated by monitoring:
 - With neurological assessment by the "Cerebral Performance Category" (CPC) score done on or in D 28, 2 months, and 1 year. (In conformance with the recommendations). This score is defined by:
 - Level 1: Conscious and good cerebral performance, might have mild neurological or psychological deficit.
 - Level 2: Conscious and moderate cerebral disability.

- Level 3: Conscious and severe cerebral disability.
- Level 4: Coma or vegetative state.
- Level 5: Brain death or demise
- For deceased patients, the number of patients progressing towards brain death, and the number of organs harvested.
- To identify predictive factors of success of pre-hospital ECMO.
- The predictive factors are obtained by clinical and para-clinical data collection (implementation of cerebral monitoring by cerebral tissue saturation, and a pupillometer as well as measurement of venous blood lactates...)

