7 NUMBER OF SUBJECTS INCLUDED

The hypothesis is that pre-hospital ECPR will result in success for 20% of the patients, considering that the percentage of survival with in-hospital use of ECMO is less than 5%. A total number of 105 patients per group will make it possible to demonstrate at the alpha risk of 5% and a power of $1-\beta=90\%$, a significant difference in favour of early pre-hospital ECPR compared to the current practice with in-hospital ECPR.

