8 STATISTICAL ANALYSIS

8.1.1 Analysis of the main judgement criterion

The success rate of pre-hospital ECMO will be compared with the percentage of success of in-hospital ECMO by a Chi-squared test. An intermediary analysis will be done every 20 patients.

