9.3 Research procedure for each patient

Baseline visit: Patient recruitment and inclusion phase

When a victim of cardiac arrest with "no flow" for less than 5 minutes is taken under care in an out-of-hospital setting, a mobile ECMO team is rushed to the spot at the 10th minute. This team verifies the inclusion criteria. The patient is included and randomised when all the eligibility criteria are met as of the 20th minute of cardiac arrest. Randomisation is done by drawing of lots from an envelope. In the pre-hospital ECMO group, treatment starts immediately. In the in-hospital ECMO group, medicalised resuscitation is continued and the patient is transferred to the hospital for the implementation of circulatory support. The ECPR success rate and implementation time are noted and compared. The family is informed at inclusion or at intensive care arrival. The patient is informed as soon as possible, if he/she is alive.

Follow-up visit on discharge from intensive care , at day 28, at 2, 6 and 12 months::

These visits should enable the evaluation of the patient outcome: survival, brain death or demise. A neurological exam evaluates the CPC score. The numbers of packed red blood cell transfusions in the first 24 hours and cases of sepsis over the course of hospitalisation are noted.

At 12 months, the physician will contact the patient to evaluate the patient outcome.

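### The primary criterion accepts ICU discharge or 6 months while the main objective is 6 months only, so the timing of the primary outcome is not fixed

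*Combined protocol and SAP*

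**What the plan says.** Section 3.1 sets the main objective as an improvement in survival "with a good neurological prognosis at 6 months evaluated by the CPC score". Section 4.1 sets the main criterion as "Patient survival with good neurological outcome (CPC 1 or 2) on discharge from the ICU or at 6 months", and the protocol summary (section 1) agrees with it: "Survival with good neurological outcome (CPC 1 or 2) on discharge from intensive care or at 6 months".

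The two time points are different visits. Section 9.3 lists them separately: "Follow-up visit on discharge from intensive care , at day 28, at 2, 6 and 12 months".

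No other section settles which one counts:

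- Section 4.2 takes CPC as a secondary criterion with the "score done on or in D 28, 2 months, and 1 year". ICU discharge and 6 months are both absent from that list, so neither has been made secondary.
- Section 7 gives rates without a time point: "pre-hospital ECPR will result in success for 20% of the patients, considering that the percentage of survival with in-hospital use of ECMO is less than" a stated ceiling of 5%.
- Section 8.1.1 gives the test without a time point: "The success rate of pre-hospital ECMO will be compared with the percentage of success of in-hospital ECMO by a Chi-squared test".

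Nowhere is it said whether *or* is a rule applied to each patient, a fallback when one assessment is missing, or a choice between two endpoints. There is no hierarchy and no split of alpha.

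**The concern.** The objective and the criterion can classify the same patient differently. Someone with CPC 2 at ICU discharge who dies in month 2 meets the criterion in section 4.1 and fails the objective in section 3.1. If the criterion is applied as written, the trial reports something other than the 6-month result it sets out to show.

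If *or* is instead taken as a choice, nothing in the plan prevents the time point from being settled once both sets of results are known. Section 6 states that blinding is impossible, so the protection has to come from the written definition. At stake are the meaning of the primary result and, under this second reading, the error rate attached to it.

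**Working it through.** **1. The plan's own figure.** Inputs from section 7: 5% versus 20%, alpha 5%, power 90%. Two-sided testing is taken from section 8.1.2. With the pooled-variance formula and no continuity correction,

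n = [1.960·√(2·0.125·0.875) + 1.282·√(0.05·0.95 + 0.20·0.80)]² / 0.15² = (0.917 + 0.584)² / 0.0225 ≈ 100.1, so 101 per group.

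Allowing for the 5% loss in section 9.6, 101/0.95 gives 107. The stated 105 lies between these, and power at 105 is 91.3% by the same approximation. The sample size is not the problem.

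**2. How each reading classifies a patient.**

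| ICU discharge | 6 months | Objective (3.1) | Discharge only | Either/or |
|---|---|---|---|---|
| CPC 1–2 | CPC 1–2 | success | success | success |
| CPC 1–2 | CPC 3–5 (5 includes death) | failure | success | success |
| CPC 3–4 | CPC 1–2 | success | failure | success |
| CPC 3–5 | CPC 3–5 | failure | failure | failure |

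The either/or reading departs from the objective in the second row, and discharge-only departs from it in the second and third.

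**3. Type I error.** If either of two tests at 5% may be called primary, the value under independence is 1 − 0.95² = 9.75%. The two outcomes are strongly correlated, so the real figure is lower. It was simulated with 105 per arm, an uncorrected chi-squared test at two-sided 5%, and 1,000,000 trials per row.

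Assumptions, none of them from the documents: a fraction l of discharge successes is lost by 6 months, with l = 10% or 20%. Patients who were not successes at discharge gain success with probability either 0 or g = p·l/(1 − p), which makes expected gains equal expected losses.

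| Rate in both arms | Change by 6 months | One time point | Better of the two |
|---|---|---|---|
| 5% | 10% lost | about 4.4% | 5.6% |
| 5% | 20% lost | about 4.4% | 6.3% |
| 5% | 10% lost, equal gain | about 4.4% | 6.2% |
| 5% | 20% lost, equal gain | about 4.4% | 7.0% |
| 12.5% | 10% lost | about 5.2% | 6.8% |
| 12.5% | 20% lost | about 5.2% | 7.5% |
| 12.5% | 10% lost, equal gain | about 5.2% | 7.4% |
| 12.5% | 20% lost, equal gain | about 5.2% | 8.2% |

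The 5% rate is the protocol's control rate; 12.5% is the average of 5% and 20%. With no change between visits there is no inflation. A single either/or test stays at about 4.4–5.2%.

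**4. Disagreement under the planned effect.** With 5% versus 20% at discharge, one time point is significant and the other is not in 4.7% and 8.8% of trials (10% and 20% lost), or 4.8% and 6.8% (equal gain added). That is about 5–9%.

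**The case against.** The strongest reply is that the plain grammatical sense of section 4.1 is a patient-level either/or, which is one endpoint with one test. On that reading type I error is controlled. No passage provides for choosing a time point afterwards, and section 3.1 can be cited to show that 6 months governs. This stands as far as error rates go. It does not remove the mismatch with the objective, and the protocol does not state that this is the intended reading.

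Four stronger readings are tempting, and the documents do not support them:

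- **That the trial has two primary endpoints, or none.** The text supports one outcome whose timing is ambiguous.
- **That a single reclassified patient decides the verdict.** With 105 per arm, 5 versus 12 successes gives p = 0.077 and 5 versus 13 gives p = 0.049. Every binary endpoint has such a boundary, including a 6-month one. With continuity correction 5 versus 13 gives p = 0.084, and at about the planned result, 5 versus 21, p = 0.0008 uncorrected.
- **That opposite verdicts are common.** At 5% versus 15% with equal loss and gain they occur in about 13–19% of trials, but the protocol plans for 5% versus 20%.
- **That the timing of ICU discharge differs between arms.** This is plausible, but nothing in the documents bears on it.

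**Conclusion.** The contradiction is in the current text and nothing in the protocol resolves it. It is an error in the definition of the primary outcome, not merely missing detail, because section 4.1 applied as written admits patients who fail the objective in section 3.1.

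The numerical consequence is conditional. There is no alpha inflation under the either/or reading. If the time point is open to choice, inflation is modest: about 5.6–7.0% at a 5% rate and 6.8–8.2% at 12.5%, with opposite verdicts in about 5–9% of trials at the planned effect. These figures rest on an assumed 10–20% loss between visits and would shrink to nothing if CPC did not change. They leave out the interim analyses in section 8.1.1, which are a separate matter. The case for correction does not depend on them: a confirmatory superiority trial needs one primary outcome, and it should match the objective.

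**What to change.** In the summary and section 4.1, state the primary outcome as: *alive with CPC 1 or 2 at 6 months after randomisation; death before 6 months is failure*.

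Add a prespecified rule for survivors with no 6-month CPC, for example failure in the main analysis and a sensitivity analysis using the last available CPC. The rule matters because section 9.6 allows up to 5% loss: 0.05 × 210 = 10.5 patients, against 105 × 0.05 + 105 × 0.20 ≈ 26 expected successes.

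Move CPC at ICU discharge to section 4.2, beside the other secondary assessments. Name the same 6-month outcome in sections 7 and 8.1.1.

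The sample size does not change, provided that 5% and 20% are meant as 6-month rates, which is how section 3.1 presents them. The 6-month visit is already planned, and the 36 months of recruitment plus one year of follow-up in section 9.5 cover it. The costs are a protocol amendment, which under section 11.4 needs sponsor approval and a favourable ethics opinion if it is substantial, and waiting for 6-month follow-up before the primary analysis.
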